6.1.2.2 Covariate-by-treatment interaction

Covariate-by-Treatment interaction will be performed on % Liver Fat at Week 16 on FAS and PPAS (observed cases) as described in section 5.2.1.4.

6.2 Secondary Endpoint(s)

The secondary endpoint will be analyzed on the FAS. All analyses will be based on observed cases.

6.2.1 Alanine Aminotransferase (ALT)

Population: Subjects with diagnosed/presumed nonalcoholic steatohepatitis, only

Endpoint: Relative change from baseline

Parameters: ALT:

- Analysis time points: **all** applicable post Day 1/Visit 5 time points where scheduled assessment of specific continuous parameter is outlined in protocol)
- Analysis population: FAS.

- Analysis methodology: Log transformed relative change from baseline will be analyzed using MMRM model with log(baseline) as a covariate (specified in section 5.2.1.2).

Reporting results:

- Raw data and percent changes from baseline: Randomized subject, number of subject contributing to summary, sample size, mean, standard deviation, median, minimum, maximum, Q1 and Q3 at baseline and post-baseline visits will be presented for each randomized arm (see Appendix 2 for further detail).
- MMRM Outputs:
 - ✓ Adjusted geometric LS mean estimates with 80% confidence interval for each randomized arm along with the translation in percent change over time,
 - ✓ Ratio of adjusted geometric LS mean estimates for each active randomized arm against placebo and the corresponding 80% confidence interval along with the translation in percent difference over time.

Figures from MMRM outputs:

1. Line plot of percent change from baseline after back transformation of adjusted geometric LS means with 80% confidence interval over time (see Appendix 3.3).
2. Line plot of percent change from baseline placebo-adjusted after back transformation of adjusted geometric LS means ratios with 80% confidence interval over time (see Appendix 3.4).
3. Percent change from baseline after back transformation of adjusted geometric LS means with 80% confidence interval at Week 16 (see Appendix 3.5).
4. Percent change from baseline placebo-adjusted after back transformation of adjusted geometric LS means ratios with 80% confidence at Week 16 (see Appendix 3.6).

Note regarding the figures:

Instead of producing 4 independent figures, and in order to having a better understanding of the placebo effect, 1 figure containing side-by-side two panels presenting bullet 1 and 2 outputs (right panel for response over time and left panel for placebo adjusted response over time), and 1 figure with two panels presenting side-by-side bullet 3 and 4 outputs (right panel for response at Week 16 and left panel for placebo adjusted response at Week 16) should be produced. Both sets of figures should start X-axis at Day 1/Baseline.

CCI

CCI

CCI

CCI

CCI

CCI

6.3.2 Tertiary Endpoints

All tertiary endpoints will be analyzed on FAS. These analyses will be based on observed cases.

6.3.2.1 Continuous Endpoints Analyzed, Over Time, on Log Scale in Subjects With Nonalcoholic Fatty Liver Disease (Entire Study Population)

Endpoint: Relative change from baseline

Parameters: CCI fasting lipid panel (ie total cholesterol, LDL-C, HDL-C, VLDL, and TG), serum apolipoprotein (ApoA1, ApoB, ApoC3, and ApoE), CCI

- Analysis time points: **all** applicable post Day 1/Visit 5 time points where scheduled assessment of specific continuous parameter is outlined in protocol)
- Analysis population: FAS
- Analysis methodology: Log transformed relative change from baseline will be analyzed using MMRM model with log(baseline) as a covariate (specified in section 5.2.1.2).

Reporting results:

- Raw data and percent changes from baseline: Randomized subject, number of subject contributing to summary, sample size, mean, standard deviation, median, minimum, maximum, Q1 and Q3 at baseline and post-baseline visits will be presented for each randomized arm (see Appendix 2 for further detail).
- MMRM Outputs:
 - ✓ Adjusted geometric LS mean estimates with confidence interval for each randomized arm along with the translation in percent change over time,
 - ✓ Ratio of adjusted geometric LS mean estimates for each active randomized arm against placebo and the corresponding confidence interval along with the translation in percent difference over time.

6.3.2.2 Continuous Endpoints Analyzed, Over Time, on Log Scale in Subjects With Diagnosed/Presumed Nonalcoholic Steatohepatitis only

Endpoint: Relative change from baseline

Parameters: CCI fasting liver function tests (ie AST, Alkaline Phosphatase, GGT, Total Bilirubin, CCI cell death biomarkers (ie CK18-M30, and CK18-M65), fibrogenesis biomarkers (ie Pro-C3, and Pro-C6), CCI :

- Analysis time points: **all** applicable post Day 1/Visit 5 time points where scheduled assessment of specific continuous parameter is outlined in protocol)
- Analysis population: FAS in subjects with diagnosed/presumed nonalcoholic steatohepatitis only
- Analysis methodology: Log transformed relative change from baseline will be analyzed using MMRM model with log(baseline) as a covariate (specified in section 5.2.1.2).

Reporting results:

- Raw data and percent changes from baseline: Randomized subject, number of subject contributing to summary, sample size, mean, standard deviation, median, minimum, maximum, Q1 and Q3 at baseline and post-baseline visits will be presented for each randomized arm (see Appendix 2 for further detail).
- MMRM Outputs:
 - ✓ Adjusted geometric LS mean estimates with confidence interval for each randomized arm along with the translation in percent change,
 - ✓ Ratio of adjusted geometric LS mean estimates for each active randomized arm against placebo and the corresponding confidence interval along with the translation in percent difference over time.

Figures from MMRM outputs

- Line plot of percent change from baseline after back transformation of adjusted geometric LS means with 80% confidence interval over time (see Appendix 3.3),
- Line plot of percent change from baseline placebo-adjusted after back transformation of adjusted geometric LS means ratios with 80% confidence interval over time (see Appendix 3.4),
- Vertical Bar chart of geometric LS means and 80% confidence interval at Week 16 (see Appendix 3.5).
- Vertical bar chart of placebo adjusted geometric LS means and 80% confidence interval at Week 16 (see Appendix 3.6).

CCI

CCI

CCI

6.3.2.4 Continuous Endpoints Analyzed on Raw Scale in Subjects With Nonalcoholic Fatty Liver Disease (Entire Study Population)

Endpoint: Change from baseline

Parameter: Glycated hemoglobin (HbA1c):

- Analysis time points : **all** applicable post Day 1/Visit 5 time points where scheduled assessment of specific continuous parameter is outlined in protocol),
- Analysis population: FAS in subjects with nonalcoholic fatty liver disease (entire study population),
- Analysis methodology: change from baseline will be analyzed using MMRM model (specified in section 5.2.1.2).

Reporting results:

- Raw data and changes from baseline: Randomized subject, number of subject contributing to summary, sample size, mean, standard deviation, median, minimum, maximum, Q1 and Q3 at baseline and post-baseline visits will be presented for each randomized arm (see Appendix 2 for further detail).
- MMRM Outputs:
 - ✓ LS mean estimates, 80% confidence interval for each randomized arm over time,
 - ✓ Differences between LS mean estimates for each active randomized arm against placebo and the corresponding 80% confidence interval over time.

6.3.2.5 Continuous Endpoints Analyzed, Over Time, on Raw Scale in Subjects With T2DM Only

Endpoint: Change from baseline

Parameters: Glycated hemoglobin (HbA1c), fasting plasma glucose (FPG), fasting plasma insulin (FPI), and HOMA-IR:

- Analysis time points: **all** applicable *post* Day 1/Visit 5 time points where *scheduled* assessment of specific continuous parameter is outlined in protocol)
- Analysis population: FAS in Subjects With T2DM only
- Analysis methodology: change from baseline will be analyzed using MMRM model (specified in section 5.2.1.2).

Reporting results:

- Raw data, and changes from baseline: randomized subject, number of subject contributing to summary, sample size, mean, standard deviation, median, minimum, maximum, Q1 and Q3 at baseline and post-baseline visits will be presented for each randomized arm randomized arm (see Appendix 2 for further detail).
- MMRM Outputs:
 - ✓ LS mean estimates, 80% confidence interval for each randomized arm over time,
 - ✓ Differences between LS mean estimates for each active randomized arm against placebo and the corresponding 80% confidence interval over time.

CCI

CCI

A large black rectangular redaction box covering the majority of the page content.

CCI

A large black rectangular redaction box covering the majority of the page content.

CCI

[figure not shown]
A large black rectangular redaction box covering the majority of the page content.

6.4 Subset Analyses

Beyond the analyses planned by 1st and 2nd tier strata (Figure 2), additional subset analyses are not planned.

Figure 2 Two-Tiered Stratification in Study C1171002

6.5 Other Summaries and Analyses

6.5.1 Standard Analyses

- Listings that account for all subjects who offered at least consent for pre-qualification and whether screen failed (at any point *after* the consent offered at the prequalification visit and *before* randomization on Day 1/Week0/Visit 5 will be presented.
- Study Conduct and Subject Disposition: The number of subjects randomized, treated, completing and discontinuing from the study, as well as the number of subjects in each analysis population will be summarized by randomized arm. The number of subjects randomized, treated, completing and discontinuing from the study, as well as the number of subjects in each analysis population will be summarized in each category of pre-defined medical history terms (ie, T2DM, Hyperglycemia, HDL increased, TG increased, hypertension, waist circumference

- increased) by randomized arm. For subjects who did not complete the study, the reasons for withdrawal from the study will be presented.
- Baseline Characteristics: Demographic characteristics such as subject age, gender, height, weight, body mass index (BMI), race, by 1st tier stratification and total per arm, by treatment group will be tabulated.
 - For each PD endpoint (ie primary, secondary or tertiary endpoint) and, as detailed in Appendix 2, baseline values will be listed and summarized by randomized arm and/or stratum and/or metabolic status (ie Type 2 Diabetes subjects vs non Type 2 Diabetes subjects). Descriptive statistics for these endpoints and derived endpoints will be also tabulated as detailed in Appendix 2.
 - Overall compliance (Day 1 to Week 16 or premature termination during treatment phase) will be summarized by frequency (%) in the following two categories by randomized arm. Formula to compute compliance is defined in Appendix 2.4.
 - < 80%
 - ≥ 80% (and up to 110%)

6.5.2 Baseline Summaries

For each endpoint (ie primary, secondary or tertiary endpoint) and, as detailed in Appendix 2, baseline values will be listed and summarized by randomized arm and/or stratum and/or metabolic status (ie subjects with versus those without Type 2 Diabetes Mellitus).

6.5.3 Concomitant Medications and Non-Drug Treatments

Number of subjects taking, at any time post randomization, medication affecting % liver fat (eg Vitamin E) will be tabulated by randomized arm.

Number of subjects under T2DM medication (T2DM), lipid medication, hypertension medication (HTN) will be tabulated by randomized arm.

For each category of medication (ie T2DM, lipid and HTN), the number of subjects receiving 0, 1, 2, or 3 medications will also be tabulated by randomized arm.

List of remaining concomitant drugs not part of the above list will only be listed.

6.6 Safety Summaries and Analyses

6.6.1 Adverse Events

Unless otherwise noted, all safety data, including the following, will be summarized descriptively by randomized dose group through appropriate data tabulations and descriptive statistics:

-
- Tier-3 adverse events will be summarized according to Pfizer standards. Tier-1 and tier 2 events will also be included in these standard summary.
 - Safety laboratory tests will be summarized according to Pfizer standards (note that actual visit window will be applied as defined in Appendix 2.1 in relation to randomized treatment).
 - ECGs will be summarized by visits. Categorical summary of ECGs will be presented according to Pfizer standards (note that baseline is defined as in section 3.4 in relation to randomized treatment).
 - Vital signs will be summarized according to Pfizer standards (note that baseline is defined as in Appendix 2. in relation to randomized treatment).
 - For the safety endpoints of special clinical concern other than AEs as defined in section 3.4.2, they will be presented with descriptive statistics as appropriate for continuous or categorical data as defined in section 5.2.
 - Hypoglycemic Adverse Event (HAE) for T2DM subjects will be characterized for each randomized arm of subjects with T2DM ***only***, as follows:
 - The number and percent of subjects reporting at least one hypoglycemic event
 - The hypoglycemic event rate, defined as the number of events reported per subject-month of treatment (per 100 subject months for severe events). Risk ratio of each active randomized arm against placebo will be displayed along with 80% CI and p-value.
 - The number of subjects with 0 event, 1 event, 2 events, 3 events, 4 events, and ≥ 5 events.
 - The median number of events per subject. P-value of each active randomized arm as compared to placebo using rank-sum test will be displayed.
 - Analysis of Tier-1 and Tier-2 TEAEs:
 - ✓ Unconditional exact test will be utilized. Risk difference will be used for the comparison.
 - ✓ No multiplicity adjustment will be made.
 - ✓ Tables and graphs will be generated. For tier-1 events, point estimates, 95% confidence intervals for the risk difference and p-values will be presented; for tier-2 events, point estimates and 95% confidence intervals for the risk difference will be presented.

- ✓ TEAEs, by preferred term, will be sorted in descending point estimate of risk difference.
- ✓ Pair-wise comparison will be made for each active randomized arm (each dose of PF-05221304) against placebo.
- ✓ For table/graphic output, include the following footnotes to provide proper interpretation of p-values and/or confidence intervals, describe how comparison is conducted. E.g. P-values and confidence intervals are not adjusted for multiplicity and should be used for screening purpose only. 95% Confidence intervals are provided to help gauge the precision of the estimates for Risk Difference. Risk Difference is computed as <PF-05221304 xx mg versus Placebo>.

It should be recognized that most studies are not designed to reliably demonstrate a causal relationship between the use of a pharmaceutical product and an adverse event or a group of adverse events. Except for select events in unique situations, studies do not employ formal adjudication procedures for the purpose of event classification. CCI

[Redacted]

6.6.2 Additional Non Standard Safety-Related Analyses to be performed:

CCI

[Redacted]

[Redacted]

CCI

A large black rectangular redaction box covering the majority of the page content.

CCI

A black rectangular redaction box covering a section of the page content.

CCI

A very large black rectangular redaction box covering almost the entire page content.A small black rectangular redaction box at the bottom of the page.

7 INTERIM ANALYSES

7.1 Introduction

*Interim analysis (IA) will be performed **at least once** while the study is on-going. This review will include an assessment of the observed safety, and observed (versus assumed) variability for the primary endpoint (liver fat via MRI-PDFF) as well as key secondary endpoint (ALT). The 1 planned IA is proposed after **at least one-third** of the total planned randomized subjects (ie, approximately 120 subjects), complete through **at least one-third** of the total dosing duration (ie, **Visit 8 [Week 6]**) of the study. Interim analysis results may be used for conducting a sample size re-estimation, stopping a dose-level for observed safety, CCI [REDACTED] and internal business decisions regarding planning of future trials with PF-05221304.*

***In addition**, during study conduct, after approximately **every** 20% of the total planned randomizations [for example: 72 subjects (20%), 145 subjects (40%), 215 subjects (60%), and 290 subjects (81%) of planned 360 subjects], based on blinded safety review by the selected members of the Sponsor's study team, unblinded review of the safety data by the IRC will be triggered and a determination of the safety to continue the study documented if post randomization **either** of the below conditions are met –*

- *More than 20% of subjects, develop a moderate or severe AE in the same system organ class (SOC);*
- *More than 15 % of subjects meet the individual permanent discontinuation of dosing rules as described in sections 3.2 of the protocol.*

7.2 Interim Analyses and Summaries

For planned interim analysis and for triggered unblinded reviews, IRC members will receive the following data summarized/analyzed by randomized arm along with the relevant subject data listings.

Study conduct and subject characteristics:

- Study conduct issues (e.g., enrollment status, currentness of the database, time between randomization and first treatment, eligibility violations)
- Subject evaluation groups
- Subject stratification factors
- Demographic and other baseline characteristics

Safety Data:

The Committee will monitor certain specific safety-related laboratory parameters, vital sign parameters, and treatment-emergent adverse events (TEAEs) as well as serious adverse events (SAEs including death) listings in an unblinded manner for overall

frequency of occurrence of events. To do so, here are the listings which should be provided:

- TEAEs (and SAEs) leading to temporary discontinuation of dosing in subjects;
- TEAEs (and SAEs) leading to permanent discontinuation and withdrawal of subjects;
- The listing of individual subject-level TEAEs and SAEs;
- All instances of hypoglycemia, or hyperglycemia, or platelet reduction, or hypertriglyceridemia leading to permanent withdrawal;
- Listing of Treatment emergent adverse events (TEAEs) under the 3-tier approach as defined in section 6.6 of this SAP;
- Listings of SAEs/deaths and narratives requested from the safety database (ie, ARGUS or similar)

CCI [REDACTED] laboratory parameters outlined in Table 2 of this SAP represent the minimum list of parameters which will be listed and provided to the committee. This list may be expanded depending on team blinded review.

The Committee will receive the distribution of subjects over time whose values cross the boundaries (ie Flag and Alert levels separately) for each of the parameters included in Table 2 of this SAP.

Percent change from baseline in other fasting lipid parameters including total cholesterol, direct low density lipoprotein cholesterol (LDL-C), very low density lipoprotein (VLDL) and high density lipoprotein cholesterol (HDL-C) will be also provided for review.

The following graphical representations of the parameters in Table 2, CCI [REDACTED] other fasting lipid parameters (see list above) will be provided:

- Individual values: median response with Q1 and Q3 per randomized arm over time, Box and whiskers plots as depicted in Appendix 3.2,
- Changes from baseline: median response with Q1 and Q3 per randomized arm over time, Box and whiskers plots as depicted in Appendix 3.2,
- Percent change from baseline: median response with Q1 and Q3 per randomized arm over time, Box and whiskers plots as depicted in Appendix 3.2

Additionally, for T2DM subjects only, graphical representation of individual values and changes from baseline in fasting plasma glucose and fasting plasma insulin over time will be provided using median response with Q1 and Q3 over time and Appendix 3.2 template.

Individual subjects' vital signs (blood pressure and pulse rate) via a listing of the raw data as well as values meeting the criteria outlined in Table 3 of this SAP will be provided.

No formal statistical analyses (eg MMRM, rank test) will be performed on safety data.

Intra- and Inter-Subject Variability Determination of % Liver Fat Using MRI-PDF and ALT variability determination:

At the time of a planned interim analysis, MRI-PDF data up to and including Day 1 (Visit 5) for all randomized subjects will be analyzed using a mixed model with week as fixed factor and subject as random factor to permit an assessment of the observed intra- and inter-subject variability in order to benchmark the results against the assumed standard deviations utilized to derive the sample size for the study.

At the time of a planned interim analysis, all data available for ALT parameter in all randomized subjects in placebo arm will be included as part of the formal internal analysis and analyzed using a mixed model with subject as random factor to permit an assessment of the observed percent change from baseline variability in the placebo arm in order to permit an assessment of whether the observed standard deviation utilized to derive the sample size for the study are in line with the assumed standard deviation for this parameter.

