## 9.1. Sample Size Determination

The sample size for this study was based on interest to assess a dose-response for effect of PF-05221304 on percent change from baseline in liver fat (entire study population as well as separately in each sub-population in 1st tier stratification) and percent change from baseline in ALT in the 1st tier stratification sub-population of diagnosed/presumed NASH.

The proposed sample size for this study is approximately 360 subjects randomized (72 subjects per arm) to ensure at least 300 subjects (60 subjects per arm) complete the study.

The sample size of a minimum of 60 completers per arm, was calculated to yield  $\geq 80\%$  power to detect a placebo-adjusted, percent change from baseline of  $\geq 30\%$  in liver fat (in entire study population *and* in  $n=30$ /arm in each sub-population of the 1st tier stratification), using a 1-sided, t-test at level 10%. The calculation assumes that the standard deviation for liver fat is 7.8% (between-subject) and 6.2% (within-subject).

For the secondary endpoint of ALT in the 1st tier stratification sub-population of diagnosed/presumed NASH, the sample size of a minimum of 30 completers per arm was calculated to yield  $\geq 80\%$  power to detect a placebo-adjusted, percent change from baseline in ALT of  $\geq 35\%$ , using a 1-sided, t-test at level 10%. The calculation assumes that the standard deviation for the parameter of placebo-adjusted, percent change from baseline in ALT is 55% (between-subject).

Overall, via the planned interim analysis (refer to [Section 9.5](#)), if the observed standard deviation for the liver fat (MRI-PDF) and ALT data, based on unblinded review, is greater than the assumptions above, the sample size for this study *may* be adjusted upward, at sponsor discretion, to a maximum of 500 subjects randomized (ie, 100 subjects per arm).

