2.2 Study Design

This is a randomized, double-blind, placebo-controlled, 5-arm (placebo, plus 4 active doses of PF-05221304), parallel-group study.

Determination of eligibility for this study will occur via a sequential, 3-step process – starting with pre-qualification. Subjects identified to be eligible based on pre-qualification will then undergo Visit 1 (Screen 1) with only those confirmed to continue to be eligible progressing to Visit 2 (Screen 2). For a given subject, this 3-step eligibility assessment (from pre-qualification to Screen 2, inclusive) may take up to 2-months.

[figure not shown]
*Once confirmed to be eligible based on Screen 2 procedure(s), subjects will progress to a run-in phase when concomitant treatment(s) will be stabilized, and baseline-related visits will occur. At Visit 5 (Day 1), subjects will be randomized to receive 1 of 5 blinded regimens for a duration of up to 16 weeks (ie, 108±4 days). Excluding the pre-qualification visit, this study includes a total of 12 scheduled outpatient visits **in the***

morning, 3 random visits for PK blood draws, **and** a potential for up to at least 3 visits for repeat assessments (for procedures/tests at Visit 1, Visit 2, or 2nd Follow-up visit). The total participation, from Visit 1 (Screen 1) to 2nd Follow-up visit, will be 27-weeks (minimum) to 35-weeks (maximum) – refer to Figure 1.

At least 360 subjects (72 per arm) will be randomized at approximately 120 sites to ensure a minimum of 300 subjects (60 per arm) complete the study. **In each arm**, ≥ 50% of subjects randomized will be deemed to be eligible for 1st tier stratification of diagnosed/presumed NASH; with the remaining subjects per arm eligible for 1st tier stratification of NAFLD with likely minimal inflammation and fibrosis (refer to Section 4.3 of the protocol for more details).

Figure 1. C1171002 Study Design

Subjects who are noted to have non-evaluable baseline MRI-PDFF, as determined by the sponsor-identified central imaging vendor, may be replaced, at sponsor discretion (refer to Section 7.1.4 of the protocol for more details); otherwise, there are no plans to replace subjects who are prematurely withdrawn. To ensure that the required minimum number of subjects complete the study, the plan is to overenroll by approximate 20% to account for premature early withdrawal.

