3.2 Secondary Endpoint(s)

- *Percent change from baseline in ALT, at Week 16 in adults with diagnosed/presumed nonalcoholic steatohepatitis, only*
- *Assessment of TEAEs, safety-related clinical laboratory tests, vital signs, and 12-lead ECGs in adults with nonalcoholic fatty liver disease (entire study population) – refer to Section 3.4, below*

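### The interim ALT variability check (SAP 7.2) uses all placebo subjects, but the ALT endpoint and its 55% SD belong to the diagnosed/presumed NASH stratum only

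*SAP*

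**What the plan says.** **The interim check.** SAP 7.2 states that "all data available for ALT parameter in all randomized subjects in placebo arm will be included as part of the formal internal analysis". The model is a mixed model with subject as random factor, and no stratum restriction or stratum term is mentioned. Its purpose is to see whether the "observed standard deviation utilized to derive the sample size for the study are in line with the assumed standard deviation for this parameter".

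**The endpoint.** SAP 3.2 defines it as "Percent change from baseline in ALT, at Week 16 in adults with diagnosed/presumed nonalcoholic steatohepatitis, only". SAP 6.2.1 repeats the limit for the analysis: "Population: Subjects with diagnosed/presumed nonalcoholic steatohepatitis, only".

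**The assumption.** Protocol 9.1 sizes ALT for the first-tier "tier stratification sub-population of diagnosed/presumed NASH, the sample size of a minimum of 30 completers per arm", with at least 80% power for a 35% placebo-adjusted change, using a one-sided t-test at 10%. The next sentence reads "The calculation assumes that the standard deviation for the parameter of placebo-adjusted, percent change from baseline in ALT is 55% (between-subject". That sentence does not name the stratum, but it describes the calculation just given for it.

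**The share of NASH subjects.** SAP 2.2 requires that in each arm "≥ 50% of subjects randomized will be deemed to be eligible for 1st tier stratification of diagnosed/presumed NASH". Up to half of the placebo arm may therefore lie outside the ALT endpoint population.

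**The consequence.** Under Protocol 9.1, if the observed SD, "based on unblinded review, is greater than the assumptions above, the sample size for this study" may be raised, at sponsor discretion, to at most 500 randomized.

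**The concern.** A variability check is useful only if the observed SD and the assumed SD describe the same population. Here they do not. The strata are also separated partly by ALT itself: outside biopsy-proven cases, Protocol 4.1 (criterion 9) places ALT above ULN and up to 5x ULN in presumed NASH, and ALT up to 1.25x ULN in the NAFLD stratum. Equal variability of percent change in ALT may hold, but the documents give no ground for assuming it.

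If NAFLD subjects vary less, they pull the pooled SD down and can hide a NASH SD above 55%. If they vary more, they can produce a signal that the endpoint population does not support. The decision at stake is an increase of up to 500 - 360 = 140 subjects.

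**Working it through.** **Inputs.** Effect 35, SD 55, 30 NASH completers per arm, one-sided alpha 10% (Protocol 9.1). Interim at about 120 subjects (SAP 7.1) in five equal arms, so 120/5 = 24 placebo subjects. The NASH share is taken at its minimum of 50%, which gives 12. The NAFLD SD is not in the documents and is varied as an assumption.

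**Step 1: reproduce the plan's figure.** Two-sample noncentral t, df = 58, noncentrality 35 / (55 × √(2/30)). Power is 87.8%, which meets the stated 80%. Solving for 80% power at n = 30 gives a largest tolerable NASH SD of 63.4.

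**Step 2: what a pooled SD of exactly 55 can conceal.** With equal stratum means and NASH share p, pooled² = p × NASH² + (1 - p) × NAFLD², so NASH SD = √((55² - (1 - p) × NAFLD²) / p).

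| NASH share | Assumed NAFLD SD | Implied NASH SD | Power, n = 30 |
|---|---|---|---|
| 50% | 30 | 71.8 | 72% |
| 50% | 40 | 66.7 | 77% |
| 50% | 50 | 59.6 | 84% |
| 50% | 55 | 55.0 | 88% |
| 60% | 30 | 66.6 | 77% |
| 70% | 30 | 62.7 | 81% |

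The implied NASH power falls below 80% only if the NAFLD SD is below about 45 at a 50% share, or below about 39 at 60%.

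Reverse case: NASH 50 and NAFLD 75 pool to √((50² + 75²)/2) = 63.7, although power at a NASH SD of 50 is 92%.

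Unequal stratum means matter little: a 20-point gap moves a common SD of 55 to √(55² + 20²/4) = 55.9.

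**Step 3: chance that the check reads above 55.** One normal value per subject. As written: SD of 12 NASH plus 12 NAFLD values (200,000 simulated replicates). Restricted: SD of the 12 NASH values, P(χ² with 11 df > 11 × 55²/SD²).

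| True NASH / NAFLD SD | As written | NASH only |
|---|---|---|
| 72 / 30 | 45% | 84% |
| 50 / 75 | 78% | 27% |
| 55 / 55 | 46% | 44% |

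**Step 4: precision.** Chi-square 95% CI around an observed SD of 55: 24 subjects (df 23) 43 to 77; 12 subjects (df 11) 39 to 93. Both intervals contain 63.4, so neither version confirms the power.

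**Step 5: what an increase would buy.** At 100 per arm, a 50% share and the planned 60/72 completion, NASH completers are 100 × 0.5 × 60/72 = 41.7 per arm. With 41, power at a NASH SD of 71.8 is 82%, against 72% with 30.

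**The case against.** **No error is demonstrated.** This stands. Percent change is already scaled to baseline, so different ALT entry ranges need not mean different variability, and the ranges overlap between ULN and 1.25x ULN. Every masking figure rests on an assumed NAFLD SD, and the 50% share is the least favourable case. It limits the size of the point, but the populations still do not match.

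**The IRC can work it out.** SAP 7.1 names the key secondary endpoint as the target, and SAP 7.2 gives the IRC stratification factors and listings that include ALT. Decision criteria are left to an IRC charter that is not among the documents. But Protocol 9.5 puts analysis details in an interim or final SAP. The SAP at hand specifies this analysis, and its wording is explicit. A separate interim SAP, if there is one, is not in the documents.

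**Restriction halves an already small sample.** True, as step 4 shows. A reader might infer that the estimate should instead pool the within-arm NASH SD over all five arms at Week 6. With about 60 subjects less five arm means (df 55), the CI around 55 narrows to 46 to 68. But SAP 6.2.1 analyses ALT as a ratio to baseline, and a multiplicative drug effect shrinks the SD of percent change. Suppose a placebo SD of 72 and a 35% reduction in all four active arms. The active SD is then 72 × 0.65 = 46.8, the pooled SD is √((72² + 4 × 46.8²)/5) = 52.8, and the chance of reading above 55 is about 32%. Pooling can thus hide the excess that the check is meant to find. It is an optional trade-off; the SAP's choice of placebo alone is sound.

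**The illustration simplifies the model.** SAP 7.2 uses all available ALT values in a mixed model, and Protocol 9.1 labels the 55% as between-subject. The one-value-per-subject figures are therefore indicative only.

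**It may be too late.** The amended SAP cites a November 2018 agreement and a count of subjects already randomized in Taiwan. This suggests, without proving, that enrolment was well advanced.

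**Conclusion.** The point holds as a mismatch of population: the stated rule tests a NASH-stratum assumption with data from both strata, and nothing else in the documents corrects it. If the strata have the same ALT variability, the mismatch does no harm. If they differ, the check can err either way.

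Two stronger readings are not supported. A reader might infer that ALT is under-powered; the plan's claim reproduces with room to spare on its own inputs. A reader might also infer that the check hides excess variability; without a NAFLD SD, a false signal is equally open.

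The consequence is moderate: ALT is a secondary endpoint and any increase is discretionary. The change is worth making because the check cannot otherwise answer its own question.

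**What to change.** In SAP 7.2, keep the placebo-arm mixed model for ALT but fit it separately by first-tier stratum. Compare only the diagnosed/presumed NASH SD with 55%. Report it with its 95% CI and a note that 80% power at 30 completers per arm holds up to an SD of about 63%. Show the NAFLD SD as description only.

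The cost is two or three sentences, with no additional subjects, visits or samples. The price is the wider interval in step 4, which should be reported openly. If the interim analysis has already been run, the NASH-only placebo SD can be reported from the same data.
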